2.3 BENEFIT/RISK ASSESSMENT

2.3.1 Risk assessment

Please refer to the master protocol for risk assessment for SAR444245, the known safety profile of the structurally similar product aldesleukin (Proleukin®) and current knowledge of the new-generation, investigational IL-2 analog NKTR-214 (bempegaldesleukin).

Risk assessment of SAR444245 when combined with pembrolizumab results from anticipated risks for SAR444245 and from the label information for Keytruda® (pembrolizumab), taking into account potential overlapping risks. The available safety data for pembrolizumab, along with proposed mitigation strategies are summarized below and also provided in [Table 11](#).

2.3.1.1 *Pembrolizumab*

Pembrolizumab potentiates T-cell responses, including antitumor responses, through blockade of PD1 binding to PD-L1 and PD-L2, which are expressed in antigen presenting cells and may be expressed by tumors or other cells in the tumor microenvironment (TME).

The use of pembrolizumab may cause IRRs (drug hypersensitivity, anaphylactic reaction, anaphylactoid reaction, and hypersensitivity). Pembrolizumab use may be associated with infections (pneumonia), bone marrow suppression (anemia, thrombocytopenia, leukopenia), increase in the level of hepatic enzymes (alanine aminotransferase, aspartate aminotransferase, alkaline phosphatase), kidney damage (nephritis, acute kidney injury), as well as adverse effects on the functioning of nervous system (dizziness, headache, peripheral neuropathy, dysgeusia (very common) and lethargy). In combination therapy with other chemotherapeutic drugs, pembrolizumab administration is commonly associated with hypertension and cardiac arrhythmia (including atrial fibrillation).

Immune-mediated adverse events are designated as important identified risks for pembrolizumab (30).

Immune-related adverse reactions, including severe and fatal cases, have occurred in patients receiving pembrolizumab. Most immune-related adverse reactions occurring during treatment with pembrolizumab were reversible and managed with interruptions of pembrolizumab, administration of corticosteroids and/or supportive care. Immune-related adverse reactions have also occurred after the last dose of pembrolizumab. Immune-related adverse reactions affecting more than one body system can occur simultaneously.

Among the immune-related AEs (irAEs) associated with pembrolizumab are: immune-related pneumonitis, immune-related colitis, immune-related hepatitis, immune-related nephritis, immune-related endocrinopathies, immune-related skin adverse reactions and other additional clinically significant, immune-related adverse reactions (reported in clinical studies or in post-marketing experience): uveitis, arthritis, myositis, myocarditis, pancreatitis, Guillain-Barré syndrome, myasthenic syndrome, hemolytic anemia, sarcoidosis, encephalitis, and myelitis.

Efficacy and safety data for pembrolizumab from patients ≥ 75 years are limited. In this population, pembrolizumab combination therapy should be used with caution after careful consideration of the potential benefit/risk on an individual basis.

Please refer to the country-approved product labeling (eg, United States Package Insert [USPI], Summary of Product Characteristics [SmPC]) for pembrolizumab for more detailed information.

2.3.1.2 SAR444245 combined with pembrolizumab

Combining SAR444245 with pembrolizumab may lead to an increased frequency and/or severity of adverse events (AEs) related to immune activation or may lead to additional AEs related to immune system activation for each substance individually or may cause occurrences of qualitatively different AEs. Serious adverse drug reactions reported with agents known to increase immune activation include pneumonitis, hepatitis, nephritis, colitis, and hormonal dysfunction (see Section 2.3.1.1).

As both substances are biologic agents, they may have the propensity to induce infusion-related reactions that may have higher rate of occurrence and severity when SAR444245 with pembrolizumab are used in combination.

The maximum tolerated dose (MTD) of SAR444245 combined with the approved dosing of the anti PD-1 pembrolizumab is under assessment in the HAMMER study using a Q3W schedule. Safety data generated from the combination of SAR444245 and pembrolizumab have informed the selection of the combination dose in this study.

2.3.2 Benefit assessment

More detailed information about the expected benefits of SAR444245 may be found in the master protocol, and the combination of SAR444245 and pembrolizumab are provided below.

In a syngeneic mouse model CT-26, relatively resistant to immune checkpoint treatment, SAR444245 potentiated the activity of an anti-PD1 antibody. Combination treatment in animals, when compared to respective monotherapies, increased the number of complete responses and prolonged survival which was durable as demonstrated by the failure of the tumor to grow upon re-engraftment on the tumor free animals, indicating the establishment of durable memory T-cell population in response to the initial treatment (see SAR444245 IB).

Immune checkpoint inhibitors are approved in most of the indications proposed to be tested in this study (please refer to [Section 2.1](#) - Study Rationale): ESCC, gastric and gastroesophageal, HCC. In gastric cancer and ESCC, the main benefit of pembrolizumab is brought to patients with diseases that have a relatively high expression of PD-L1 (CPS ≥ 10). Combining SAR444245 to pembrolizumab is anticipated to expand to population responding to the an anti-PD1 and to increase the quality of the response. Such effects have been demonstrated in the PIVOT-02 study for bempegaldesleukin combined with nivolumab in metastatic melanoma, achieving deep and durable responses with rates of CR of 34% and PFS (30.9 months) exceeding that reported in clinical trials for approved treatments ([31](#)). Objective responses were also documented in PDL1 negative cases (n=13), with an ORR of 39% and 3 patients achieving 100% reduction of target lesions, and 2 patients achieving CR. Echoing these results are those of the same combination in 1L metastatic urothelial carcinoma, an indication where response to immune checkpoint is linked to the level of expression of PD-L1. In this study, bempegaldesleulin when combined with nivolumab induced significant ORR with 17% CR, with ORR similar and PD-L1 negative (50%) and PD-L1 positive (56%) ([15](#)), which contrast with data from Keynote-052 for pembrolizumab ([32, 33](#)). Combining SAR444245 with pembrolizumab is anticipated to bring benefit to patients with ESCC and GC/GEJ even in the context of low PD-L1 and could rescue patients who have progressed or relapsed following an anti-PD1/PD-L1.

2.3.3 Overall benefit: risk conclusion

More detailed information about the expected benefits of SAR444245 may be found in the master protocol.

Taking into account the measures taken to minimize risk to participants in this study, the potential risks identified in association with this new generation IL-2 SAR444245 combined with the anti-PD1 inhibitor pembrolizumab are justified by the anticipated benefits that may be afforded to participants with GC/GEJ.

2.3.4 Benefit and risk assessment in the context of COVID-19 pandemic

Please refer to the master protocol for more details about risks related to the patient population, SAR444245 treatment, and study related activity.

In addition, the impact of PD-1 blockade therapy on Coronavirus disease 2019 (COVID-19) severity was also explored by 2 groups and did not find a clinically meaningful signal ([34, 35](#)).

3 OBJECTIVES AND ENDPOINTS

Please refer to the master protocol for description of common objectives and endpoints. Substudy-specific objectives and endpoints are summarized below.

Table 1 - Objectives and endpoints

Objectives	Endpoints

3.1 APPROPRIATENESS OF MEASUREMENTS

Please refer to the master protocol.

4 STUDY DESIGN

4.1 OVERALL DESIGN

Cohorts B1, B2 and B3 will assess SAR444245 adding on to pembrolizumab in participants with advanced unresectable or metastatic gastric cancer (GC) or Siewert Type 2 & 3 gastro-esophageal junction adenocarcinoma (GEJ) and for whom receiving standard of care (SOC) is not in his or her best interest (for example, participants who are not eligible, cannot tolerate, decline to receive, or have no access to such treatment) or where no SOC is established. MSI-H cases will not be eligible. HER2 + cases will not be eligible unless they have progressed on a trastuzumab-based treatment.

- *Cohorts B1 & B2* participants must not have received more than two prior lines of treatment that did not include an anti-PD1/PD-L1-based regimen. Participants will be assigned to one of these 2 cohorts according to the level of PD-L1 expression at baseline using the CPS as follow:
 - *Cohort B1*: participants with CPS ≥ 1 GC/GEJ
 - *Cohort B2*: participants with CPS < 1 GC/GEJ
- *Cohort B3* participants are eligible regardless of the disease CPS status and must have received at least one and no more than three prior lines of treatment and have progressed after primary or secondary resistance to an anti-PD1/PD-L1-based regimen (detailed in [Section 5.1](#)).

Please refer to the master protocol for a full description of the study design, and for details applicable to all therapy cohorts.

A graphical presentation of the substudy schema is shown in [Figure 1](#). For treatment period, the completion of Cycle 35 is applicable for Cohorts B1, B2, and B3.

4.2 SCIENTIFIC RATIONALE FOR STUDY DESIGN

The proposed substudy aims to establish proof-of-concept that combining the non-alpha-IL2 SAR444245 with the anti-PD1 antibody pembrolizumab will result in a significant increase in the population experiencing an objective response.

The design of the study is a non-randomized study where the experimental combination will be assessed in a single cohort for each indication, using historical data for single agent immune-checkpoint, as a benchmark to show outstanding objective response rate. The ORR will be assessed using RECIST 1.1 for participants with advanced unresectable and metastatic GC/GEJ.

Please refer to the master protocol for more information.

4.2.1 Participant input into design

There was no participant input into design of the trial.

4.3 JUSTIFICATION FOR DOSE

4.3.1 SAR444245 dose

Please refer to the master protocol.

4.3.2 Pembrolizumab dose

The planned dose of pembrolizumab for this study is 200 mg every 3 weeks (Q3W). Based on the totality of data generated in the Keytruda development program, 200 mg Q3W is an appropriate dose of pembrolizumab for adults across all indications. As outlined below, this dose is justified by:

- Clinical data from 8 randomized studies in melanoma and NSCLC indications demonstrating flat dose- and exposure-efficacy relationships from 2 mg/kg Q3W to 10 mg/kg every 2 weeks (Q2W) representing an approximate 5 to 7.5 fold exposure range (refer to the pembrolizumab IB).
- Population PK analysis showing that both fixed dosing and weight-based dosing provides similar control of PK variability with considerable overlap in the distributions of exposures, supporting suitability of 200 mg Q3W
- Clinical data showing meaningful improvement in benefit-risk including overall survival at 200 mg Q3W across multiple indications. And
- Pharmacology data showing full target saturation in both systemic circulation (inferred from PK data) and tumor (inferred from physiologically-based PK [PBPK] analysis) at 200 mg Q3W.

Among the 8 randomized dose-comparison studies, a total of 2262 participants were enrolled with melanoma and NSCLC, covering different disease settings (treatment naïve, previously treated, PD-L1 enriched, and all-comers) and different treatment settings (monotherapy and in combination with chemotherapy). Five studies compared 2 mg/kg Q3W versus 10 mg/kg Q2W (KN001 Cohort B2, KN001 Cohort D, KN002, KN010, and KN021), and 3 studies compared 10 mg/kg Q3W versus 10 mg/kg Q2W (KN001 Cohort B3, KN001 Cohort F2 and KN006). All of these studies demonstrated flat dose- and exposure-response relationships across the doses studied representing an approximate 5- to 7.5- fold difference in exposure. The 2 mg/kg (or 200 mg fixed-dose) Q3W provided similar responses to the highest doses studied. Subsequently, flat dose-exposure-response relationships were also observed in other tumor types including head and neck cancer, bladder cancer, gastric cancer and classical Hodgkin Lymphoma, confirming 200 mg Q3W as the appropriate dose independent of the tumor type. These findings are consistent with the mechanism of action of pembrolizumab, which acts by interaction with immune cells, and not via direct binding to cancer cells.

Additionally, pharmacology data clearly show target saturation at 200 mg Q3W. First, PK data in KN001 evaluating target-mediated drug disposition (TMDD) conclusively demonstrated saturation of PD1 in systemic circulation at doses much lower than 200 mg Q3W. Second, a PBPK analysis was conducted to predict tumor PD1 saturation over a wide range of tumor penetration and PD1 expression. This evaluation concluded that pembrolizumab at 200 mg Q3W achieves full PD1 saturation in both blood and tumor.

Finally, population PK analysis of pembrolizumab, which characterized the influence of body weight and other participant covariates on exposure, has shown that the fixed-dosing provides similar control of PK variability as weight-based dosing, with considerable overlap in the distribution of exposures from the 200 mg Q3W fixed dose and 2 mg/kg Q3W dose. Supported by these PK characteristics and given that fixed-dose has advantages of reduced dosing complexity and reduced potential of dosing errors, the 200 mg Q3W fixed-dose was selected for evaluation across all pembrolizumab protocols.

4.4 END OF STUDY DEFINITION

Please refer to the master protocol.

5 STUDY POPULATION

See the master protocol for a full list of common inclusion and exclusion criteria and the subsections below for Cohorts B1, B2, and B3 specific criteria.

5.1 INCLUSION CRITERIA

Participants are eligible to be included in the study only if all of the following criteria apply (in addition to the criteria listed in the master protocol):

Type of participant and disease characteristics

I 01. Histologically or cytologically confirmed diagnosis of GC or Siewert Type 2 & 3 GEJ.

I 02. Confirmed diagnosis at study entry of advanced unresectable or metastatic disease.

PD-L1 expression using CPS as determined at local laboratory with an approved test (please refer to the lab manual for details on PD-L1 assay)

I 03. *For participants in Cohort B1:* Disease with CPS scoring of ≥ 1 .

I 04. *For participants in Cohort B2:* Disease with CPS scoring of < 1 .

Note: *For participants in Cohort B3:* Disease with any CPS scoring. No need for CPS determination at local laboratory.

I 05. MSI status: Participants must have MSI status known, determined locally and must have non-MSI-H disease to be eligible.

I 06. Other genetic aberrations: Participants with unknown HER2/neu status must have their HER2/neu status determined locally. Participants with HER2/neu negative are eligible. Participants with HER2/neu positive tumors must have documentation of disease progression on treatment containing trastuzumab to be eligible.

Prior anticancer therapy

I 07. *For participants in Cohorts B1, and B2:* Participants for whom available SOC should not be in their best interest and should have failed or relapsed on no more than 2 prior lines of treatment, and which did not include an anti-PD-1/PD-L1-based treatment. See instructions specific to Korea in Appendix 7 (Section 10.7).

I 08. *For participants in Cohort B3:* Participants should have received at least one but no more than 3 prior lines of treatment, including an anti-PD-1/PDL-1 containing regimen and have progressed after a primary or secondary resistance to an anti-PD-1/PDL-1. See instructions specific to Korea in Appendix 7 (Section 10.7).

Note: For Cohorts B3:

Primary resistance is defined as a patient who has experienced progressive disease (PD) or SD lasting <6 months of initiation of PD-1/PD-L1 inhibitor-based treatment and who received at least 6 weeks of the PD1/PD-L1. Radiographic confirmation of the PD must be documented after a minimum of 4 weeks after the initial identification of progression, unless: i) investigator confirms clinical progression/ deterioration attributed to PD, or ii) the first radiographic assessment indicated critical tumor growth by imaging (size or location).

Or

Secondary resistance: patients must have experienced PD, either during or within 3 months of discontinuing treatment with anti-PD1-based therapy, occurring after previous clear benefit (any complete [CR] or partial response [PR]), or after previous stable disease (SD) >6 months. No requirement for radiographic confirmation of progression.

I 09. An anti-PD1/PD-L1 containing regimen is defined as either an anti-PD1/PD-L1 monotherapy, or an anti-PD1/PD-L1 agent administered in the same cycle as another systemic anticancer therapy. If PD1/PD-L1 was used beyond initial radiological progression while continuing to use the same PD1/PD-L1 agent used before PD, it is still considered as the same regimen. The site's study team must have reviewed previous tumor assessments (including screening tumor imaging) to determine that radiographic progression has occurred per RECIST 1.1 following initiation of the anti-PD1/PD-L1 containing regimen.

I 10. Provision of tumor tissue:

- **Mandatory baseline biopsy** for participants in **Cohorts B1, B2, and B3**,: minimum 5 slides with 4-5 micron thickness for the first 20 participants who have signed ICF (excluding screen failure participants), minimum 10 slides with 4-5 micron thickness for subsequent participants in each cohort. Archival tumor tissue samples should be obtained from biopsies done within 6 months, and there should be no systemic anti-cancer therapy between collection of biopsy and enrollment. Slides specifications are detailed in Lab Manual.
- **Optional on-treatment biopsy** for Cohorts B1, B2, and B3 per Investigator's discretion and evaluation.
- The Sponsor may approve the written request to enroll, on a case-by-case basis, participants with:
 - location of the tumor not amenable to biopsy due to significant risk, OR
 - less than required number of slides or archival tumor tissue sample collected more than 6 months prior to enrollment.

5.2 EXCLUSION CRITERIA

Participants are excluded from the study if any of the following criteria apply (in addition to the criteria listed in the master protocol):

Prior/concomitant therapy

E 01. For participants in Cohorts B1 and B2: Prior treatment with an agent (approved or investigational) that blocks the PD-1/PD-L1 pathway (participants who joined a study with an anti-PD-1/PD-L1 but have written confirmation they were on control arm are allowed).

5.3 LIFESTYLE CONSIDERATIONS

Please refer to the master protocol.

5.4 SCREEN FAILURES

Please refer to the master protocol.

5.5 CRITERIA FOR TEMPORARILY DELAYING ENROLLMENT/RANDOMIZATION/ADMINISTRATION OF STUDY INTERVENTION

Please refer to the master protocol.

6 STUDY INTERVENTION(S) AND CONCOMITANT THERAPY

6.1 STUDY INTERVENTION(S) ADMINISTERED

Please refer to the master protocol.

For study treatment duration, completion of Cycle 35 is applicable for Cohorts B1, B2, and B3.

Dosing sequence:

In addition, if a participant has immune unconfirmed progression of disease (iUPD) and is clinically stable, it is at the discretion of the Investigator to continue treating the subject with the assigned treatment per protocol until progression of disease is confirmed (iCPD) at least 4 weeks, but no longer than 8 weeks from the date of the scan suggesting progression of disease (Section 10.9).

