p CT/MRI: The initial tumor imaging will be performed within 28 days prior to C1D1. Scans performed as part of routine clinical management are acceptable for use as the screening scan if they are of diagnostic quality and performed within 28 days prior to the date of enrollment. On study imaging will be performed every 9 weeks (63 ± 7 days) after the date of first IMP and if clinically indicated. Imaging studies should follow calendar days and should not be adjusted for delays in cycle starts or extension. The same imaging technique should be used in a participant throughout the trial. After week 45, tumor imaging should be performed every 12 weeks (84 ± 7 days). CT scan of the chest, abdomen, pelvis and any other locations with suspicion or evidence of disease involvement is required for the baseline assessment, during treatment period until PD. Per the primary tumor assessment criteria, after the first documentation of response or the first documentation of progression (if the participant is clinically stable), confirmatory imaging may be performed no fewer than 28 days later. Alternately, the scan performed at the next scheduled time point (eg, every 63 ± 7 days) may be used as confirmation. Tumor assessment is not needed for participants who start another anti-cancer therapy.

q [REDACTED]
[REDACTED]

Abbreviations: ADA=anti-drug antibodies; AE=adverse event; AST=aspartate transaminase; ALT=alanine transaminase; C=Cycle; ANC=Absolute neutrophil count; AP=Alkaline phosphatase; BUN=Blood urea nitrogen; CRF=case report form; CRS=Cytokine release syndrome; CT=computed tomography; [REDACTED] D=Day; ECG=electrocardiogram; ECOG=Eastern Cooperative Oncology Group; e-CRF=electronic case report form; EOT=end-of-treatment; FT4=free thyroxine; FU=follow-up; HBsAg=Hepatitis B surface antigen; HCV=Hepatitis C virus; ICF=Informed consent form; IMP=investigational medicinal product; INR=international normalized ratio; LDH=Lactate hydrogenase; LVEF=left ventricular ejection fraction; MRI=magnetic resonance imaging; MUGA= multigated acquisition; PD=progressive disease; [REDACTED]; PDy=pharmacodynamic; PK=pharmacokinetic; [REDACTED]; PR=partial response; PS=Performance Status; SpO2=oxygen saturation; Q3W=every 3 weeks; RECIST=Response Evaluation Criteria in Solid Tumors; SAE=serious adverse event; T3=tri-iodothyronine; TSH=thyroid stimulating hormone; WBC=White blood cells.

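### Substudies 02 and 04: the scheduled scan that the Schedule of Activities accepts for confirming progression usually falls after the 8-week limit in Section 6.1

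*Protocol*

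**What the plan says.** **Section 6.1, substudies 02 and 04 (same sentence in both).** The rule on treatment past first progression reads: "if a participant has immune unconfirmed progression of disease (iUPD) and is clinically stable, it is at the discretion of the Investigator to continue treating". Treatment may go on until progression is confirmed "at least 4 weeks, but no longer than 8 weeks from the date of the scan suggesting progression of disease". The sentence ends by pointing to Section 10.9, which is redacted.

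**Section 1.3, Schedule of Activities, footnote p (same text in both substudies).** The footnote applies to a first response and also to "the first documentation of progression (if the participant is clinically stable". For either event, "confirmatory imaging may be performed no fewer than 28 days later". It then gives a second route: "Alternately, the scan performed at the next scheduled time point (eg, every 63 ± 7 days) may be used as confirmation". It sets no upper limit.

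**Scan calendar, same footnote.** "On study imaging will be performed every 9 weeks (63 ± 7 days) after the date of first IMP and if clinically indicated". Later the interval lengthens: "After week 45, tumor imaging should be performed every 12 weeks (84 ± 7 days". Footnote b fixes the imaging dates from Cycle 1 Day 1 and does not move them when treatment is delayed.

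Substudy 03 (Cohort C) has the same footnote p, but its visible Section 6.1 carries no sentence on treatment past unconfirmed progression. The point is therefore limited to substudies 02 and 04.

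**The concern.** Both passages address a clinically stable participant whose scan has just shown progression for the first time. They agree that confirmation may not come before 4 weeks. Section 6.1 closes the period at 8 weeks, whereas footnote p leaves it open and names a scan that, on the protocol's own calendar, normally arrives after 8 weeks.

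A site that plans its imaging from the Schedule of Activities can choose the scheduled scan in good faith, keep treating until it, and so pass the limit in Section 6.1. A site that works from Section 6.1 would not. How long participants are treated beyond a first progression scan could then differ between sites according to which page was followed, and conduct that footnote p allows could be recorded as a deviation from Section 6.1.

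**Working it through.** **Inputs**

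- Limit on confirmation (Section 6.1): 4 to 8 weeks.
- Scan interval up to week 45 (footnote p): 9 weeks, stated as 63 ± 7 days.
- Scan interval after week 45 (footnote p): 12 weeks, stated as 84 ± 7 days.
- Scan dates fixed from Cycle 1 Day 1 (footnote b), so each scheduled scan has its own ±7-day window.

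**The plan's own figures.** 9 × 7 = 63 and 12 × 7 = 84, so the stated day counts reproduce. The limit is 4 × 7 = 28 to 8 × 7 = 56 days.

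**Formula.** Suppose the first scan is *a* days and the next scan *b* days from its nominal date, each between −7 and +7. The gap between two scheduled scans is then

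gap = nominal interval + *b* − *a*.

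**Up to week 45 (nominal 63 days)**

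- Nominal excess: 63 − 56 = 7 days.
- First scan on its nominal day: gap 56 to 70 days. Only the earliest of the 15 window days (day 56) meets the limit.
- Both windows in use: 63 − 14 = 49 to 63 + 14 = 77 days.
- The limit is met only if *a* − *b* ≥ 7. Of the 15 × 15 = 225 whole-day combinations, 8 + 7 + 6 + 5 + 4 + 3 + 2 + 1 = 36 do so, or 16%. This is a count of possible dates, not a probability, because real scan dates need not be spread evenly over their windows.

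**After week 45 (nominal 84 days, for example week 45 to week 57)**

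- Nominal excess: 84 − 56 = 28 days.
- First scan on its nominal day: 77 to 91 days.
- Both windows in use: 84 − 14 = 70 to 84 + 14 = 98 days.
- Meeting the limit would need *a* − *b* ≥ 28, but the largest possible value is 14. None of the 225 combinations complies.

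**When the first scan is unscheduled.** Footnote p also provides for imaging when clinically indicated. If such a scan at week 51 shows progression, the scheduled scan at week 57 is nominally 6 × 7 = 42 days later and inside the limit. The results above therefore hold only where both scans are scheduled.

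**The case against.** The strongest reply is that the two passages can both be obeyed. Footnote p is permissive. A confirmatory scan between day 28 and day 56 satisfies it and Section 6.1 together, and the scheduled-scan route remains useful for confirming responses and for participants not treated past progression. The passages also use different language: footnote p refers to the primary tumor assessment criteria, and Section 4.2 assesses ORR by RECIST 1.1, while Section 6.1 speaks of iUPD and iCPD. This stands as far as it goes: a compliant path exists. It does not remove the problem, because footnote p offers the scheduled scan as an equal alternative for a clinically stable participant with first progression, and no visible text closes that option to someone being treated under Section 6.1.

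The second reply is that the reconciling rule may sit in the redacted Section 10.9 or in the master protocol, to which Section 6.1 defers. That is possible, and it limits confidence. If such a rule exists, what remains is a missing cross-reference in footnote p.

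A reader might also infer more than the documents support:

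- *That a scheduled scan after week 45 can never confirm in time.* Not so when the first scan was unscheduled, as the week 51 example shows.
- *That the overshoot amounts to a fixed number of extra doses.* The gap varies (98 − 56 = 42 days at its widest), and in Cohort D2 cetuximab is given weekly rather than every 3 weeks. No single count fits all five cohorts.
- *That immune-criteria response or PFS results are affected.* The relevant exploratory sections and Section 10.9 are redacted, and nothing visible ties ORR to the 8-week limit.
- *That later confirmation is invalid.* Section 6.1 limits continued treatment; it does not say that a later scan cannot confirm progression.

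**Conclusion.** The inconsistency is real in the visible text of substudies 02 and 04 and affects Cohorts B1, B2, B3, D1 and D2. Between two scheduled scans, the confirmation route in footnote p exceeds the 56-day limit by a nominal 7 days up to week 45, where it usually but not always misses, and by a nominal 28 days after week 45, where it always misses. What is at stake is the length of study treatment after a first progression scan and its uniformity across sites. No sample-size or error-rate figure depends on it.

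The conclusion assumes that footnote p applies to participants treated under Section 6.1, which its wording allows and nothing visible denies, and that neither Section 10.9 nor the master protocol already settles the matter. The arithmetic is certain; whether the conflict is resolved in text that cannot be seen is not. It is worth correcting on those terms.

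**What to change.** Reconcile Section 6.1 and footnote p in substudies 02 and 04 so that one confirmation interval applies to participants treated past unconfirmed progression. State in footnote p whether the scheduled-scan option is available to those participants, and refer from there to Section 6.1. If Section 10.9 or the master protocol already contains the governing rule, a cross-reference to it from both places is enough. Which interval applies, and how confirmation is obtained within it, is for the sponsor's clinical team.

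The drafting cost is about a sentence in each substudy. Any change to the number or timing of scans would depend on the interval chosen.
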